- Algorithm 1 (paper algorithm): dose adjustment guidance provided (Section 10.8); study participant will receive an initial individualized LY3209590 dose on Day 1 with weekly adjustments based on fasting glucose (FG) and hypoglycemia data for the first 12 weeks, then every 4 weeks.

For patients randomized to LY3209590 Algorithm 1, documented guidance for dose adjustment is provided (Section 10.8).

For patients randomized to the insulin degludec arm the following guidance for administration is applicable:

Insulin degludec will be self-administered daily by participants after a training and first administration under site personnel supervision on Day 1 according to a modified Riddle algorithm (Section 10.8).

General considerations

Study procedures will be performed as listed in the Schedule of Activities (Section 1.3).

To allow timely sampling for PK assessments, visits for collection of the samples will be scheduled within the required time windows provided in the Schedule of Activities.

Participants will continue to use concomitant metformin (alone or in combination with a stable dose of a DPP4V inhibitor and / or a SGLT2 inhibitor) throughout the treatment period. Discontinuation or changes to dose are not permitted, except in situations where dose adjustment or complete discontinuation is required per country-specific label or when allowed per study protocol (for further details, see Section 6.5.2).

Self Monitoring of Blood Glucose (SMBG): All measurements have to be recorded in the provided electronic diary. Participants will be instructed to perform FG measurements each day. In addition, two 6-point SMBG profiles (prior to and 2 hours after the morning, midday, and evening meals) should be done on nonconsecutive days in the week prior to the required visits noted in the Schedule of Activities (Section 1.3).

Participants who develop severe, persistent hyperglycemia based on prespecified thresholds (see Section 6.1.2.3) will receive a new glucose-lowering intervention (or rescue therapy) based on clinical judgment of the investigator (see table in Section 6.5). Participants who need rescue therapy will continue on IP in the trial until they complete all study visits.

Flash glucose monitoring (FGM): Participants will undergo 3 FGM sessions using the LibrePro System (Abbott) in the 14-day period prior to randomization, Visit 15, and Visit 20. Patients will remain blinded to these assessments until the study is completed.

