Study Period 3: End-of-Treatment and Safety Follow-up, Visits 20, 801, Early Discontinuation 1 and 2 (ED1 and ED2)

All randomized participants should have a comprehensive efficacy and safety evaluation at Visit 20 and a safety follow-up visit approximately 6 weeks after the last dose of LY3209590 and 5 weeks after the last dose of insulin degludec. During the safety follow-up study period, participants will continue SMBG and may be treated with an appropriate glucose-lowering regimen (see table in Section 6.5) if appropriate. Participants will also be required to return the study diary and used or unused IP to the investigative site.

Participants who *complete the treatment period* will have a comprehensive End-of-Treatment efficacy and safety assessment (Week 26; Visit 20). The safety follow-up assessment (Visit 801) should occur approximately 5 weeks after their End-of-Treatment assessment (Visit 20). Participants will also be required to return used and unused IP as well as the study diary to the investigative site at V801.

Participants who *discontinue IP prior to completion* of the treatment period for any reason should also have a comprehensive End-of-Treatment efficacy and safety assessment (early discontinuation [ED]1) approximately 1 week after the last dose of LY3209590 or as soon as reasonably possible thereafter, and should have a safety follow-up assessment (ED2)

approximately 5 weeks after ED1. Study activities at Visits ED1 and ED2 are identical to Week 26 (Visit 20) and Visit 801, respectively. CCI

and the switch to an alternative, commercially available insulin must be closely monitored to prevent hypoglycemia due to an accumulation of insulin action.

Participants who discontinue IP prior to the completion of the treatment period will be encouraged to remain in the study and to complete any scheduled study procedures until Visit 20. Participants remaining in the study will receive an appropriate glucose-lowering regimen. Table in Section 6.5 provides details on the use of glucose-lowering medications, which can be used.

Participants who *discontinue IP for any reason and are unwilling to return for a safety follow-up* visit, will be asked to perform an early termination (ET) visit as their final study visit. At this visit, participants will perform procedures listed in the Schedule of Activities (Section 1.3).

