6.1.2.3. Management of Patients with Severe, Persistent Hyperglycemia During the Treatment Period

An additional therapeutic intervention should be considered in patients who develop severe, persistent hyperglycemia after randomization based on the following criteria (FDA 2008):

- a) average FG > 270 mg/dL (> 15.0 mmol/L) over any 2-week period or longer during the first 6 weeks postrandomization; or
- b) average FG > 240 mg/dL (> 13.3 mmol/L) over any 2-week period or longer from Week 6 to Week 12 postrandomization; or
- c) average FG > 200 mg/dL (> 11.1 mmol/L) over any 2-week period or longer after Week 12.

Investigators should first confirm that the patient does not have an acute condition causing severe hyperglycemia and, after the first 12 weeks of the study, that the patient is fully compliant with the assigned therapeutic regimen. The investigator will decide, in consultation with the patient, on an appropriate glucose-lowering intervention (rescue intervention) after considering relevant clinical criteria. See table in Section 6.5 for allowed medications. Patients who receive a new intervention for hyperglycemia management should also continue administering IP for the remaining period in the trial.

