Patients who stop the IP permanently may receive another glucose-lowering intervention, if appropriate, and will continue participating in the trial according to the protocol to collect all planned efficacy and safety measurements.

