7.2. Participant Discontinuation/Withdrawal from the Study

A participant will be discontinued (withdrawn) from the study in the following circumstances:

- if he or she is diagnosed with any type of diabetes mellitus other than T2DM
- at any time at his/her own request
- at the discretion of the investigator for safety, behavioral, compliance, or administrative reasons
- if the participant becomes pregnant during the study
- if enrollment in any other clinical study involving an IP or enrollment in any other type of medical research judged not to be scientifically or medically compatible with this study
- participation in the study needs to be stopped for medical, safety, regulatory, or other reasons consistent with applicable laws, regulations, and good clinical practice (GCP)
- investigator decision
 - the investigator decides that the participant should be discontinued from the study

- if the participant, for any reason, requires treatment with another therapeutic agent that has been demonstrated to be effective for treatment of the study indication, discontinuation from the study occurs prior to introduction of the new agent
- participant decision:
 - the patient or the patient's designee, for example, parents or legal guardian requests to be withdrawn from the study.

Discontinuation is expected to be uncommon.

At the time of discontinuing from the study, if possible, an early discontinuation visit should be conducted, as shown in the Schedule of Activities (Section 1.3). See Schedule of Activities for data to be collected at the time of study discontinuation and follow-up and for any further evaluations that need to be completed. The participant will be permanently discontinued both from the study intervention and from the study at that time.

If the participant withdraws consent for disclosure of future information, the sponsor may retain and continue to use any data collected before such a withdrawal of consent. If a participant withdraws from the study, he/she may request destruction of any samples taken and not tested, and the investigator must document this in the site study records.

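### Protocol 7.2 withdraws anyone who needs another effective agent, while 4.1.1, 6.1.2.3 and 7.1.1 keep such participants in the study; the passages must be reconciled

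*Protocol*

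**What the plan says.** Protocol 7.2 lists the circumstances in which a participant is withdrawn from the study. One is that the participant requires, for whatever reason, another agent shown to be effective for the study indication. In that case "discontinuation from the study occurs prior to introduction of the new agent". The section then says: "The participant will be permanently discontinued both from the study intervention and from the study at that time". It contains no carve-out for rescue therapy or for treatment given after study drug has been stopped. It does not say which section prevails in a conflict.

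Four other statements give a different instruction.

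- Section 4.1.1, on rescue: "Participants who need rescue therapy will continue on IP in the trial until they complete all study visits".
- Section 6.1.2.3, on severe persistent hyperglycemia: "Patients who receive a new intervention for hyperglycemia management should also continue administering IP for the remaining period in the trial".
- Section 4.1.1, on participants who stop study drug early: they "will be encouraged to remain in the study and to complete any scheduled study procedures until Visit 20", and "Participants remaining in the study will receive an appropriate glucose-lowering regimen".
- Section 7.1.1, on permanent discontinuation of study drug: such patients "may receive another glucose-lowering intervention, if appropriate, and will continue participating in the trial according to the protocol", the stated purpose being "to collect all planned efficacy and safety measurements".

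SAP 5.7 defines a supportive estimand for the Week 26 HbA1c change that disregards rescue use and whether study drug is still being taken. It uses whatever Week 26 data exist, and fills endpoints lost through early study discontinuation by return-to-baseline imputation.

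**The concern.** A participant who meets the hyperglycemia criteria and needs a new class of glucose-lowering drug falls under both instructions. Section 7.2 takes that participant off drug and off study before the new drug starts; 4.1.1 and 6.1.2.3 keep the same participant on drug and on study. A participant who has stopped study drug and needs other treatment faces the same conflict between 7.2 on one side and 4.1.1 and 7.1.1 on the other.

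Two things are at stake. The first is consistent conduct. The trial is open-label, rescue is a matter of investigator judgment, and Appendix 1 (10.1.1) requires deviations to be reported within 5 working days. As written, a site that follows either instruction departs from the other.

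The second is the Week 26 measurement. The early discontinuation visit that 7.2 requests, where possible, includes HbA1c, but it is taken when the participant leaves, not at Week 26. The supportive analysis would then treat the endpoint as missing and impute it, although its estimand exists to capture outcomes after rescue or after stopping study drug. The later measurements that 4.1.1 and 7.1.1 intend would also be lost.

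**Working it through.** **The passages side by side**

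| Situation | Protocol 7.2 | Other sections |
|---|---|---|
| New agent needed while on study drug | Off drug and off study, before the agent starts | 4.1.1 and 6.1.2.3: stays on drug and in the trial |
| New agent needed after stopping study drug | Off study, before the agent starts | 4.1.1: encouraged to stay to Visit 20 on other treatment; 7.1.1: continues in the trial |

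All of this is current text, not amendment history. Two further places lean towards retention but carry less weight. Section 6.5.1 allows named rescue classes and short-term emergency insulin during the study. For other new agents it asks for the drug to be stopped and a deviation report, not for withdrawal. Appendix 10 supplies alternative treatment through safety follow-up, but only for pandemic or disaster disruption.

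**The plan's own figures**

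Protocol 9.2 gives margin 0.4, SD 1.1, true difference 0, two-sided alpha 0.1 and 100 completers per arm.

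- Standard error = 1.1 × √(2/100) = 0.1556.
- Power = Φ(0.4/0.1556 − 1.645) = Φ(0.926) = 82.3%, which agrees with the stated figure of more than 80%.
- Randomized = 200/(1 − 0.20) = 250, as stated.

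Reconciling the passages changes neither figure.

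**Illustrative effect on the supportive analysis**

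The documents give no rescue rate, so these inputs are assumptions:

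- n = 125 per arm (the randomized number in protocol 9.2);
- the unobserved Week 26 change would have been a fall of d, with d from 0 to 1.0 points;
- return-to-baseline imputation replaces it with a mean change of 0;
- k is the net excess of affected participants in one arm.

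Shift in the treatment difference = k × d/125.

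| k | d = 0 | d = 0.5 | d = 1.0 | d = 1.0, as share of CI half-width |
|---|---|---|---|---|
| 1 | 0 | 0.004 | 0.008 | 3.5% |
| 5 | 0 | 0.02 | 0.04 | 17% |
| 10 | 0 | 0.04 | 0.08 | 35% |

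The last column compares the shift with the approximate 90% CI half-width, 1.645 × 1.1 × √(2/125) = 0.229.

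The shift goes against the arm with the excess. Equal numbers with similar lost change give about zero. If the unobserved values were above baseline, the direction reverses.

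**The case against.** The strongest reply is that 7.2 is one general line in a list of withdrawal reasons, while every passage that deals with rescue by name points to retention. Sites would probably follow the specific text. That is plausible, and it limits the likely number of affected participants. It does not settle the matter, because the protocol never says that the specific text prevails and 7.2 is worded as mandatory.

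Some of the other points stand:

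- Raising an existing metformin dose, or the dose of another existing oral drug, introduces no new agent. That part of rescue falls outside the 7.2 line.
- Appendix 10 and 6.5.1 are weak support, and the contradiction does not need them.
- The documents give no basis for expecting an excess of 5 or 10 in one arm. The fasting-glucose thresholds for rescue are high, both arms are titrated to the same fasting target, and 7.2 itself expects discontinuation to be uncommon. The table shows scale; it is not evidence of bias.
- The 125 per arm is approximate. The supportive analysis takes all randomized and dosed patients with a baseline value. If former Algorithm 2 participants are included, the LY3209590 group is larger and each participant's effect smaller.
- The SAP 5.7 rule for the supportive analysis can be run under either instruction. What depends on 7.2 is how many values it observes and how many it imputes.

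The primary analysis also needs a careful statement. Protocol 9.4.3 already drops data after rescue or after stopping study drug, so it loses nothing. The primary data sentence in SAP 5.7 cuts off only at treatment discontinuation. Read literally, it would admit HbA1c values recorded after rescue while still on drug. That mismatch is a separate item, which changing 7.2 would not cure.

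**Conclusion.** The contradiction is real and should be fixed. Withdrawal and retention cannot both be the instruction for a participant who needs a new glucose-lowering agent, and nothing in the protocol ranks one above the other. The textual conflict is certain; the size of its consequence is not.

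On the stated assumptions the supportive difference moves by at most 0.008 points per net affected participant. That analysis carries no margin test. The non-inferiority conclusion under protocol 9.4.3 and the stated power are unaffected. The case for acting rests on clear site conduct and on keeping the Week 26 values the supportive estimand was written to use, not on a demonstrated bias. No view is taken here on which clinical rule is right.

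**What to change.** Reconcile the 7.2 line with 4.1.1, 6.1.2.3, 6.5.1, 7.1.1 and Appendix 10, so that sites have a single instruction on whether participants who start another glucose-lowering agent stay in the study. It should cover both those still on study drug and those who have stopped it. The sponsor chooses the clinical rule.

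Then add a line to SAP 5.7 saying which Week 26 values the supportive analysis will observe and which it will impute under that instruction.

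The cost is one sentence in a protocol amendment or clarification letter and matching SAP wording, with no new visits or data.

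Separately, align the SAP 5.7 primary data sentence with protocol 9.4.3 on whether data after rescue are excluded.

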7.2.1. Discontinuation of Inadvertently Enrolled Participants

If the sponsor or investigator identify a participant who did not meet enrollment criteria and was inadvertently enrolled, then the participant should be discontinued from study treatment unless there are extenuating circumstances that make it medically necessary for the participant to continue on study treatment. If the investigator and the sponsor clinical research physician (CRP) agree it is medically appropriate to continue, the investigator must obtain documented approval from the sponsor CRP to allow the inadvertently enrolled participant to continue in the study with or without treatment with IP. Safety follow-up is as outlined in Section 1.3 (Schedule of Activities), Section 8.3 (Adverse Events and Serious Adverse Events), and Section 8.2 (Safety Assessments) of the protocol.

7.3. Lost to Follow-up

A participant will be considered lost to follow-up if he or she repeatedly fails to return for scheduled visits and is unable to be contacted by the study site.

The following actions must be taken if a participant fails to return to the clinic for a required study visit:

- The site must attempt to contact the participant and reschedule the missed visit as soon as possible and counsel the participant on the importance of maintaining the assigned visit schedule and ascertain whether or not the participant wishes to and/or should continue in the study.
- Before a participant is deemed lost to follow-up, the investigator or designee must make every effort to regain contact with the participant (where possible, 3 telephone calls and, if necessary, a certified letter to the participant's last known mailing address or local

equivalent methods). These contact attempts should be documented in the participant's medical record.

- Should the participant continue to be unreachable, he/she will be considered to have withdrawn from the study.

Discontinuation of specific sites or of the study as a whole are handled as part of Section [10.1](#).

8. Study Assessments and Procedures

Study procedures and the study visits at which they are performed, including tolerance limits for the study visits, are listed in the Schedule of Activities (Section 1.3). Adherence to the study design requirements, including those specified in the Schedule of Activities, is essential and required for study conduct.

Efficacy and safety assessments included in this study are generally regarded as reliable and accurate with respect to the efficacy and safety assessments in individuals and populations with T2DM.

8.1. Efficacy Assessments

8.1.1. Primary Efficacy Assessments

The primary efficacy measure is HbA1c change from baseline to Week 26.

8.1.2. Secondary Efficacy Assessments

Secondary efficacy assessments for this study are:

- HbA1c change from baseline to Week 12
- FG change from baseline to Weeks 12 and 26.

8.2. Safety Assessments

Planned time points for all safety assessments are provided in the Schedule of Activities, Section 1.3.

The following safety assessments will be evaluated as secondary objectives:

- Incidence and rate of hypoglycemia
- Incidence of treatment-emergent SAEs
- Clinical laboratory assessments with specific focus on liver aminotransferase changes.

8.2.1. Physical Examinations

A complete physical examination will include, at a minimum, assessments of the CV, Respiratory, Gastrointestinal and Neurological systems. Height and weight will also be measured and recorded.

Investigators should pay special attention to clinical signs related to previous serious illnesses. Additionally, investigators should inspect injection sites during the physical examination.

8.2.2. Vital Signs

For each participant, vital signs measurements should be conducted according to the Schedule of Activities (Section 1.3).

Sitting blood pressure (BP) and pulse rate will be measured using automated electronic sphygmomanometer according to the Schedule of Activities (Section 1.3). Vital sign measurements should be taken before obtaining an ECG tracing and before collection of blood

samples for laboratory testing, at visits where required (see Schedule of Activities, Section 1.3). The participant should be required to sit quietly for 5 minutes before vital sign measurements are taken. An appropriately sized cuff (cuff bladder encircling at least 80% of the arm) should be used to ensure the accuracy of BP measurements. The arm used for the BP measurement should be supported at heart level. Blood pressure should be measured consistently using the same arm throughout the study. For each parameter (pulse rate, systolic BP, and diastolic BP), 3 measurements will be taken using the same arm; the recordings should be taken at least 1 minute apart, and each measurement of sitting pulse rate and BP will be recorded in the eCRF.

8.2.3. Electrocardiograms

For each patient, triplicate 12-lead digital ECGs and single safety ECGs will be collected according to the Schedule of Activities (Section 1.3). Patients must be supine for approximately 5 to 10 minutes before ECG collection and remain supine but awake during ECG collection. ECGs will be performed prior to collection of any blood samples.

ECGs will be interpreted by a qualified physician (the investigator or qualified designee) at the site as soon as possible after the time of ECG collection, and ideally while the patient is still present, to determine whether the patient meets entry criteria at the relevant visit(s) and for immediate patient management should any clinically relevant findings be identified.

Digital ECGs will be electronically transmitted to a central ECG laboratory designated by Lilly. The central ECG laboratory will perform a basic quality control check (for example, demographics and study details) then store the ECGs in a database. At a future time, the stored ECG data may be overread at the central ECG laboratory for further evaluation of machine-read measurements or to meet regulatory requirements.

The machine-read ECG intervals and heart rate may be used for data analysis and report writing purposes unless an overread of the ECGs is conducted prior to completion of the final study report (in which case the overread data would be used).

8.2.4. Self-monitoring of Blood Glucose (SMBG)

At Visit 2, patients will receive plasma-equivalent glucose meters and strips. SMBG readings should be performed for monitoring patient safety (hypoglycemia) and may be checked as frequently as necessary. Patients should record all SMBG measurements in the study diary provided. Patients with missing SMBG values may need to be retrained on the importance of SMBG monitoring.

Patients will also measure FG daily and as needed to evaluate symptoms of hypoglycemia.

Patients will be instructed to perform 6-point SMBG profiles over a 24-hour period on 2 nonconsecutive days during the 7-day period prior to visits indicated in the Schedule of Activities (Section 1.3). The 6-point profile consists of pre-meal and 2-hour postprandial SMBG measurements for the morning, midday, and evening meals in 1 day. Pre-meal measurements should be taken before the patient begins eating the meal. Patients should record their glucose measurements in their study diaries and bring the diary to the investigative site at each study visit.

